## 10.5.1.2 Adverse Event Definitions

An AE is any unfavorable or unintended change in body structure (signs), body function (symptoms), laboratory result (e.g., biochemistry, ECG, etc.), or worsening of a pre-existing condition associated temporally with the use of the study drug whether or not considered related to the study drug.

A treatment-emergent AE is any condition that was not present prior to treatment with study drug but appeared following treatment, was present at treatment initiation but worsened during treatment, or was present at treatment initiation but resolved and then reappeared while the individual was on treatment (regardless of the intensity of the AE when the treatment was initiated).

All AEs, including either observed or volunteered problems, complaints, signs, or symptoms must be recorded on the AE page of the CRF, regardless of whether associated with the use of study drug. This would include AEs resulting from concurrent illness, reactions to concurrent medication use, or progression of disease states (excluding the disease under study). AEs should be recorded in standard medical terminology.

The Investigator will evaluate each AE for duration, intensity, and relationship to study drug, record the action taken, and any treatment given. Recurrent symptoms of a chronic pre-existing condition are not considered AEs unless they occur in a worse or unexpected pattern during study drug administration.

### 10.5.1.3 Intensity of AEs

The intensity (or severity) of AEs is characterized as mild, moderate, or severe:

**Mild** AEs are usually transient, requiring no special treatment, and do not interfere with the subject's daily activities.

**Moderate** AEs introduce a low level of inconvenience or concern to the subject and may interfere with daily activities, but are usually ameliorated by simple therapeutic measures.

Severe AEs interrupt a subject's usual daily activity and typically require systemic drug therapy or other treatment.

When the intensity category of the AE changes more frequently than once daily, the maximum intensity for the event is recorded. If the intensity category changes after a number of days, then these sub-events or changes are recorded separately (i.e., having distinct onset and stop dates).

### 10.5.1.4 Relationship to Study Drug

The degree of "relatedness" of the AE to the study drug may be described using the following scale:

Not related indicates that the AE is definitely not related to the study drug.

**Unlikely related** indicates that there are other, more likely causes and study drug is not suspected as a cause.

**Possibly related** indicates that a direct cause and effect relationship between study drug and the AE has not been demonstrated but there is a reasonable possibility that the event was caused by the study drug.

**Probably related** indicates that there probably is a direct cause and effect relationship between the AE and the study drug.

It is the Sponsor's policy to consider "Probable" and "Possible" causality assessments as positive causality. It is the Sponsor's policy to consider "Not" and "Unlikely" causality assessments as negative causality.

Assessments are to be recorded on the CRF and must indicate clearly the relationship being assessed.

### 10.5.1.5 Serious Adverse Event

An SAE is defined as an AE that:

- Results in death
- Is immediately life-threatening (there is an immediate risk of death from the AE as it occurred; this does not include an AE that had it occurred in a more serious form may have caused death)
- Results in or prolongs an inpatient hospitalization (Note: a hospitalization for elective or pre-planned surgery, procedure, or drug therapy does not constitute an SAE unless there is a complication resulting in hospitalization prolongation). An AE that results in a visit to an Emergency Room that does not require an inpatient stay is not always classified as an SAE.
- Results in permanent or substantial disability (permanent or substantial disruption of one's ability to conduct normal life functions)
- Is a congenital anomaly/birth defect (in offspring of a patient using the study drug regardless of time to diagnosis)
- Is considered an important medical event

Life-threatening events are defined as events that place the subject, in the view of the Investigator, at immediate risk of death from the reaction as it occurred, i.e., it does not include a reaction that, had it occurred in a more severe form, might have caused death.

Disability is defined as a substantial disruption of a person's ability to conduct normal life functions.

Important medical events are defined as events that, based upon appropriate medical judgment, may jeopardize the subject and may require medical or surgical intervention to prevent one of the outcomes. Examples of important medical events include allergic bronchospasm requiring intensive treatment in an emergency room or at home, blood dyscrasias or convulsions that do not result in inpatient hospitalization, or the development of drug dependency or drug abuse.

#### 10.5.2 Pregnancy

Pregnancies among study participants or their partners should be reported to the Sponsor or designee as soon as possible after learning of the event. Subjects who become pregnant will not receive any more CAM2038 doses, will be discontinued from the study and referred back to the care of their usual provider or continue in the study after discussion with and documentation by the Investigator or his/her designee. Follow-up information will be obtained where possible (with the consent of the participant or their partner) regarding the course and outcome of the pregnancy, including any post-natal sequelae in the infant.

#### **10.5.3 Clinical Laboratory Assessments**

All protocol-specified laboratory tests on blood and urine samples will be performed at a selected laboratory. The lab will generate laboratory reports and forward them to the CRU in a timely manner. It is the responsibility of the Investigator to review and sign all laboratory reports expeditiously, in order to document appropriate safety monitoring of study subjects. The Investigator should sign and date each laboratory report concurrent with her or his review, and should indicate the clinical significance of each abnormal/flagged value by noting "NCS" (not clinically significant) or "CS" (clinically significant), for example. Notations indicating that a value is clinically significant should also include a brief description of the underlying disease or condition that is associated with the value, e.g., "CS/mild anemia." In general, abnormal, clinically significant laboratory values are expected to be associated with an item recorded in medical history or with an AE.

Blood and urine samples will be collected, processed, and shipped according to instructions from the safety laboratory. Additional laboratory samples may be taken at the discretion of the Investigator if the results of any tests fall outside reference ranges or clinical symptoms necessitate testing to ensure safety. Specific hematology, coagulation, biochemistry, and urinalysis assessments are listed in Table 4. Of note, a targeted assessment of electrolytes will be conducted throughout the study at pre-specified time points, and at additional time points at the discretion of the Investigator.

Hematology	Biochemistry	Urinalysis
Hematocrit	Sodium	12 panel illicit drug screen
Hemoglobin	Potassium	Color
Red blood cell count	Magnesium	pH
Red blood cell morphology	Calcium	Specific gravity
Mean corpuscular volume	Glucose (random)	Ketones
Mean corpuscular hemoglobin	Bicarbonate	Protein
Mean corpuscular hemoglobin	Chloride	Glucose
concentration	Creatinine	Bilirubin
Total and differential (absolute)	Total protein	Nitrite
white blood cell count	Blood urea nitrogen	Urobilinogen
Platelets	Albumin	Occult blood
Coagulation	Total bilirubin	Microscopic examination of
	Alanine transferase	sediment, only if urinalysis
Prothrombin time, International	Aspartate transferase	dipstick results are abnormal
normalized fatio	Lactic dehydrogenase	
	Amylase	
	Lipase	
	Gamma-glutamyl transferase	
	Alkaline phosphatase	
	Creatine phosphokinase	
	Total cholesterol (non-fasting)	

In addition to the clinical laboratory tests, a serum pregnancy test will be performed at the Screening and EOT visits. A urine pregnancy test will be required prior to all doses of CAM2038 q1w and q4w for all women of childbearing potential. Results must be reviewed and confirmed to be negative prior to start of CAM2038 treatment (Day 1).

The approximate total blood volume, including PK sample collections (Section 10.3.1.1) to be taken per subject during the study is the following:

- Group 1 total blood volume: approximately 546 mL
- Group 2 total blood volume: approximately 382.5 mL
- Group 3 total blood volume: approximately 352.5 mL

#### 10.5.4 Vital Signs

Vital signs will consist of temperature, blood pressure (systolic and diastolic blood pressure, mmHg), pulse rate (beats per minute), and respiratory rate (breaths/min) collected while sitting, following a rest period of at least 3 minutes. Vital signs will be measured at the time points

Clinical Study Protocol Braeburn Pharmaceuticals HS-15-549 CONFIDENTIAL specified in Table 1 (Group 1), Table 2 (Group 2), and Table 3 (Group 3). Clinically significant values will be recorded as AEs.

#### 10.5.5 12-Lead Electrocardiogram

12-Lead ECGs will be performed after the subject has been resting in a recumbent/supine position for at least 3 minutes at the times specified in Table 1 (Group 1), Table 2 (Group 2), and Table 3 (Group 3). The ECG variables will include ventricular heart rate and the PR, QRS, QT, QTcF intervals. The ECGs will be signed and dated by a medically-qualified individual to confirm review of the ECG and verify whether any abnormalities are clinically significant. In general, abnormal, clinically significant ECGs are expected to be associated with an item recorded in medical history or with an AE. Subjects who have QTc > 500 msec or post-baseline increase > 60 msec will be discontinued from the study and will not receive any more injections of CAM2038. Subjects will then have daily ECGs until QTc values return to baseline. The Investigator can refer the subject to a Cardiologist, if necessary.

#### **10.5.6 Physical Examination**

A complete physical examination including all major body systems will be performed at Screening and EOT visits.

Height, weight and BMI will be determined at the Screening visit. Weight and BMI will also be determined at the EOT visit.

#### **10.5.7 Injection Site Examination**

All CAM2038 injection sites (new and old) will be examined during each scheduled visit after the first dose of CAM2038 for any signs of adverse site reactions, including erythema, pruritus, edema, pain, etc. Injection site examination form is included in Appendix 17.3. Subjects will also be queried specifically about local tolerability AEs in connection to the examinations. Non-identifying photographs will be taken to document any injection site reactions.

#### 10.5.8 Columbia-Suicide Severity Rating Scale

The C-SSRS will be used to assess both behavior and ideation. The C-SSRS tracks all suicidal events, and provides a summary of suicidal ideation and behavior. It assesses the lethality of attempts and other features of ideation (frequency, duration, controllability, reasons for ideation, and deterrents), all of which are significantly predictive of completed suicide.

Two versions of the C-SSRS will be used in this study: the Baseline/Screening version (6 months and lifetime history; Appendix 17.4) and the Since Last Visit version (Appendix 17.5). The Screening version of the C-SSRS will be administered at Screening. The Since Last Visit version of the C-SSRS will be administered at all subsequent assessment times, as indicated in Table 1 (Group 1), Table 2 (Group 2), and Table 3 (Group 3).

The C-SSRS is to be administered by the Investigator or his/her qualified designee. Qualified designee is defined has completed the C-SSRS training within the last 2 years. The survey should be administered by the same assessor, where possible, throughout the study.

#### Clinical Study Protocol HS-15-549 **10.5.9 Subjective Opioid Withdrawal (SOWS) Scale**

In the SOWS, subjects rate the intensity of each of 16 common motoric, autonomic, gastrointestinal, musculoskeletal, and psychic symptoms of opioid withdrawal on a 5-point Likert scale, i.e., from 0 ("not at all") to 4 ("extremely"), based on how they were feeling at the time of testing (Appendix 17.6).

### 10.5.10 Clinical Opioid Withdrawal (COWS) Scale

Study personnel will assess clinical observations indicative of withdrawal using the COWS (Appendix 17.7). This scale consists of 11 common opioid withdrawal signs or symptoms, rated on a numeric scale and based on a timed period of observation of the subject by the rater.

#### **10.5.11 Treatment Identification Card**

Subjects will receive a wallet card indicating that they are receiving BPN as part of the study. This card should be presented to health care providers by the subject in the event of an emergency or if medications such as opioid analgesics are required. Sample wallet cards will be provided for IRB submission.

#### **10.5.12 Other Safety Considerations**

BPN may impair the mental and physical abilities required for performance of potentially dangerous tasks. Subjects will be instructed to avoid operating heavy machinery during induction and to exercise caution in performing activities requiring alertness such as driving a car during the first few days until such time that they are reasonably certain that their ability to engage in such activities is not adversely affected.

#### **10.6 Efficacy Variables**

#### **10.6.1 Urine Toxicology**

The frequency and incidence of urine toxicology results positive for opioids other than BPN, and positive results for other, non-opioid, drugs of abuse will be measured via qualitative methods.

#### 10.6.2 Numerical Rating Scale for Pain

The weekly average of daily Pain Intensity (PI) will be calculated based on non-missing NRS scores (i.e., the missing daily scores will not be used in the calculation for the average). This weekly average will be called PI for that week. Pain Intensity Difference (PID) for a post-baseline Week i will then be derived as

PID at week 1i = PI at baseline – PI at week i.

Based on this definition, a positive PID is indicative of an improvement. The efficacy endpoint will be the change from Baseline in the weekly average of the daily Worst Pain score.

### 10.7 Appropriateness of Measures

The primary objective of this study is to evaluate steady state PK of CAM2038 q1w following SC injection at various administration sites and steady state PK of CAM2038 q4w; therefore, PK

Clinical Study Protocol Braeburn Pharmaceuticals HS-15-549 CONFIDENTIAL blood samples will be collected to assess plasma concentrations of BPN and norBPN and derive the necessary PK parameters to evaluate rate and extent of exposure.

Standard safety outcomes, such as AEs, vital signs and clinical laboratory testing will be assessed during the study. In addition, frequent ECG assessments will be included to monitor potential QTc interval prolongation following repeated administration of CAM2038 q1w and q4w. The COWS and SOWS are included to monitor any potential opioid withdrawal symptoms associated with transitiong from SL BPN to CAM2038 and throughout the study.

Exploratory measures include urine toxicology and pain NRS scores, which are typical of studies evaluating efficacy in managing opioid dependence and chronic pain.

# 11 DATA QUALITY ASSURANCE

This study will be conducted under Good Clinical Practice (GCP) and all applicable regulatory requirements. To ensure compliance, the Sponsor, or designee, may conduct a quality assurance audit, as outlined in Section 11.2.

Actions to ensure the accuracy and reliability of data include the selection of qualified investigators and appropriate study centers; the review of protocol procedures with the Investigator and study personnel prior to study start; the design of suitable source documents with appropriate instructions for use (where applicable); the internal audit of source data according to GCP and internal procedures to ensure their accuracy, completeness, and verifiability; as well as the periodic site monitoring by the Sponsor. The Sponsor, or designee, will review source documents for accuracy and completeness during on-site monitoring visits and after their return to the Sponsor; any discrepancies will be resolved with the Investigator, as appropriate.

Significant and/or repeated non-compliance will be investigated and remedial action instituted when appropriate. Failure to comply with remedial actions may result in investigational site termination and regulatory authority notification.

## 11.1 Data Collection

Source documents include but are not limited to original documents, data and records such as hospital/medical records (including electronic health records), clinic charts, laboratory results, participant diaries, data recorded in automated instruments, microfilm or magnetic media, and pharmacy records, etc. This study will use electronic data capture (EDC). At a minimum, all data required by the protocol should have supporting source documentation for entries in the EDC system.

All CRFs will be completed by the site staff prior to review by the Sponsor's monitor or designated representative. The Sponsor's monitor or designated representative will review all source records on-site and compare them to the data collected on the CRF. All entries, corrections, and alterations will be made by the Investigator or other authorized study personnel. All data entries will be verified for accuracy and correctness by independent monitors. The EDC system maintains a full audit trail.

### 11.2 Study Auditing and Monitoring

Monitoring of the study site (including, but not limited to, reviewing CRFs for accuracy and completeness) will be performed by the Sponsor's designated monitor(s). The extent, nature, and frequency of on-site visits will be based on such considerations as the study objectives and/or endpoints, the purpose of the study, study design complexity, and enrollment rate. By signing the protocol, the Investigator agrees that, within local regulatory restrictions and institutional and ethical considerations, authorized representatives of the Sponsor, a regulatory authority, and/or an IRB may visit the site to perform audits or inspections, including the drug storage area, study drug stocks, drug accountability records, participant charts and source documents, and other

Clinical Study Protocol

HS-15-549

records related to study conduct. The purpose of the Sponsor audit or inspection is to systematically and independently examine all study-related activities and documents to determine whether the study-related activities were conducted and data recorded, analyzed, and accurately reported according to the protocol, the site's standard operating procedures, GCP guidelines of the International Conference on Harmonisation (ICH), and any applicable regulatory requirements. The Investigator should contact the Sponsor immediately if contacted by a regulatory agency regarding an inspection.

# 12 STATISTICAL METHODS AND DETERMINATION OF SAMPLE SIZE

### 12.1 Statistical and Analytical Plans

Complete details of the statistical analyses to be performed will be documented in a SAP. The SAP may include more detail of analysis populations, summary strategies, and any clarifications or changes necessary due to, for example, regulatory requests. The SAP must be finalized before database lock. Any changes to the final SAP will be discussed in the final study report.

### **12.2 Analysis Populations**

Three study populations are defined.

- Safety population: All subjects who receive at least part of an injection of the study medications. All safety analyses will be based on the Safety population.
- **Pharmacokinetic population**: The PK population will consist of all subjects in the Safety population who have provided sufficient PK data for all 4 randomized injection sites to derive PK parameters of interest (Group 1), or have provided PK data after the last injection of CAM2038 q4w (Group 2 and Group 3). All PK summaries will be based on the PK population.
- Efficacy population: The efficacy population will be the intent to treat population consisting of all subjects that have received at least 1 injection of CAM2038 and provided some efficacy measures.

### 12.3 Planned Analyses

#### 12.3.1 Demographics and Other Baseline Characteristics

Disposition for all enrolled subjects will be summarized. Reasons for discontinuation will be tabulated. Demographic data and baseline psychosocial characteristics will be summarized by sequence and overall. The summaries will be performed by group, and sequence if appropriate.

Tabular summaries and/or listings will be provided for baseline clinical characteristics, such as illicit drug and treatment use history, medical history, inclusion/exclusion criteria, and medication history.

#### 12.3.2 Analysis of Pharmacokinetics

Summaries of plasma concentrations of BPN and norBPN will be presented for the PK population by Group, treatment, and injection site, if applicable. The following descriptive statistics will be presented at each nominal timepoint: n, arithmetic mean, standard deviation, and coefficient of variation percentage (CV%), median, geometric mean, geometric CV%, minimum and maximum values. Mean plasma concentration-time data will be displayed for the PK population in linear and semi-logarithmic scales by Group, treatment and injection site, if applicable. Individual plasma concentrations of BPN and norBPN will be listed for the Safety population by Group, treatment, and injection site, if applicable.

Clinical Study Protocol

HS-15-549 CONFIDENTIAL For Group 1 (CAM2038 50 mg/mL q1w), the following considerations will apply in the PK analyses. The primary PK parameters will be AUCss and Css,max after steady state injections of CAM2038 q1w at different injection sites. The injection site buttock will be the reference. The analyses will be based on log-transformed data. The natural log-transformed AUCss and Css,max data will be analyzed using an ANOVA model, sequence, subject within sequence (1, 2, 3, 4 corresponding to A/B/D/C, B/C/A/D, C/D/B/A, D/A/C/B, where A=buttock, B=abdomen C=thigh, or D=back of upper arm), period, and treatment (treatment sites: A=buttock, B=abdomen C=thigh, or D=back of upper arm). The estimated treatment effects, treatment differences versus the reference (B-A, C-A, and D-A), and the 90% confidence intervals of the estimated differences will be presented. The above estimates will be expressed on the raw scale (expressed after performing the anti-log). All other PK parameters will be summarized by descriptive statistics.

For Group 2 (CAM2038 q4w) and Group 3 (CAM2038 q4w and SL BPN), the PK parameters will be summarized by descriptive statistics. The primary PK parameters will be AUCss and Css,max.

The PK parameters (Section 10.3.2) will be listed for the Safety population and summarized by Group, treatment, and injection site, if applicable, for the PK population. Summary statistics will include: n, arithmetic mean, standard deviation, CV%, median, geometric mean, geometric CV%, minimum and maximum values.

#### 12.3.3 Analysis of Safety

Exposure will be summarized by Group, treatment, and injection site, as applicable.

AEs will be coded by primary system organ class (SOC) and preferred term according to the Medical Dictionary for Regulatory Activities (MedDRA), and summarized by number and percent of subjects in each primary SOC and preferred term by Group. Summaries of these AE subsets will be presented for relationship to study drug, intensity, seriousness, AEs or SAEs leading to discontinuation. Frequencies for deaths and hospitalizations will also be summarized by Group and overall. Injection specific AEs will also be summarized.

Data for clinical laboratory tests, ECG, vital signs, and physical and injection site examinations will be summarized by Group using standard descriptive and change from baseline statistics. Shift tables and tabular summaries of abnormalities will be provided by Group, where appropriate.

The average SOWS and COWS scores over the Treatment Phase and average change from baseline (Day 1) SOWS and COWS scores will be presented.

Medications will be coded using the World Health Organization Drug dictionary and may be summarized by Group using descriptive statistics.

By-subject listings will be provided for all safety data.

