## 5.0 ANALYSIS POPULATIONS

## 5.1 SAFETY POPULATION

The safety population will include all subjects who have received study medication. Analyses based on this population will group subjects according to the treatment they actually received regardless of the treatment they are randomized to receive. All safety analyses will use the safety population.

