# **11.0** SUMMARIES OF MEASURES OF SAFETY

Safety analyses will be performed for the safety population. Safety evaluations will be based on the incidence, intensity, and type of adverse events, as well as on clinically significant changes in the subject's physical examination, vital signs, and clinical laboratory results, Injection site examination and wound care. Safety variables will be tabulated and presented by study drug actually received.

Because there is no pre-specified safety outcome defined in terms of AEs, clinically relevant laboratory parameters, or vital signs, any formal comparisons between the treatment arms with respect to specific safety parameters will be post-hoc.

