## **11.1** EXTENT OF EXPOSURE

Summary statistics (number and percentage) of weeks of exposure to study drug (i.e. from date of initial injection to the end of the study) will be tabulated by treatment group.,

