## **11.4** ADVERSE EVENTS

Each AE and SAE term recorded on the case report forms (CRFs) by primary system organ class (SOC) and will be mapped to a preferred term using the MedDRA dictionary. The investigator will assess AE severity and relationship to the study treatment.

A treatment emergent adverse event (TEAE) is defined as any AE with an onset date on or after date of randomization (Groups 1 and 2) or first SL BPN dose (Group 3), or any ongoing event on the date of first dose that worsens in severity after date of randomization. Only TEAEs with an onset date prior to date of last dose + 30 days will be tabulated in summary tables. For the purpose calculating treatment emergence and inclusion in summary tables, incomplete onset dates will be imputed as detailed in Appendix A.

TEAEs will be summarized by the number and percent of subjects in each primary SOC and preferred term. Subjects will be counted only once for each primary SOC and each preferred term. Summary tables of TEAEs by primary SOC, preferred term and intensity will be provided. If a subject has more than one TEAE coded to the same preferred term, the subject will be counted only once for that preferred term by using the event with the highest intensity. Similarly, if a subject has more than one TEAE within a primary SOC category, the subject will be counted only once in that SOC category by using the event with the highest intensity. TEAEs by primary SOC, preferred term and relationship to study drug will be provided as well. If a subject has more than one TEAE coded to the same preferred term, the subject will be counted only once for that preferred term by using the most related event. Similarly, if a subject has more than one TEAE within a primary SOC category by using the most related event. In addition, serious adverse events (SAE) by primary SOC and preferred term will be provided. Deaths and SAEs will be summarized similarly to AEs. All adverse event tables will also include the total number of events, counting multiple events per subject.

Injection related TEAEs, Other (non-injection related) TEAEs as well as all TEAEs will be presented by treatment group and overall. Summaries of these TEAE subsets will be presented for the following categories:

- Study drug related
- Intensity
- Relationship to injection
- Serious
- AEs which led to discontinuation
- SAEs which led to discontinuation
- TEAEs occurring in 5% or greater of any treatment group (by preferred term)

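### Group 3 TEAEs and COWS/SOWS averages pool the sublingual run-in week with the CAM2038 period, because nothing assigns events by onset or sets a pre-injection baseline

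*Protocol*

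**What the plan says.** Protocol 7.1 and Table 3 put the seven daily 24 mg SL BPN doses on Days 1 to 7 and the 160 mg CAM2038 injections on Days 8, 36, 64 and 92. Table 3 places the SL days inside the Treatment Phase.

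- **TEAEs.** SAP 11.4 defines a TEAE as "any AE with an onset date on or after date of randomization (Groups 1 and 2) or first SL BPN dose (Group 3", closing bracket omitted. For tabulation it says: "Injection related TEAEs, Other (non-injection related) TEAEs as well as all TEAEs will be presented by treatment group and overall". Protocol 12.3.3 also summarizes AEs by group.
- **Exposure.** SAP 11.1 counts "weeks of exposure to study drug (i.e. from date of initial injection to the end of the study". In Group 3 that starts on Day 8, a week after the TEAE window opens.
- **Safety population.** SAP 5.1: "The safety population will include all subjects who have received study medication". Protocol 12.2 is narrower: "All subjects who receive at least part of an injection of the study medications".
- **Presentation of safety data.** SAP 11.0: "Safety variables will be tabulated and presented by study drug actually received".
- **COWS/SOWS.** Protocol 12.3.3: "The average SOWS and COWS scores over the Treatment Phase and average change from baseline (Day 1) SOWS and COWS scores will be presented". SAP 11.3 asks for both scales over time by treatment group and names no baseline and no Treatment Phase average. Protocol 10.7 says the scales are there to monitor "any potential opioid withdrawal symptoms associated with transitiong from SL BPN to CAM2038".

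**The concern.** The safety and tolerability of CAM2038 is a secondary objective. In Groups 1 and 2 the first study treatment is CAM2038, so the TEAE window and the Day 1 baseline both sit at the switch from SL BPN. In Group 3 both sit a week before it. Followed as written, the plan puts events that began on SL BPN into the Group 3 column with events that began after injection. A subject who leaves during the SL week also qualifies for the SAP safety population without having received CAM2038.

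The scales meant to monitor the switch are averaged over a phase that starts seven days before it, against a baseline from the start of that week. A withdrawal signal after the first injection would be diluted in that summary, and the Group 3 column would not describe the same thing as the Group 1 and 2 columns beside it.

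**Working it through.** The plan states no figure on this point, so there is none to reproduce. The inputs are Table 3, its footnotes and the SAP 11.4 window.

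**COWS/SOWS count, Group 3.** The Table 3 footnote requires scoring before each dose on dosing days.
- Before the first injection: Days 1 to 7 plus Day 8 pre-dose = 8.
- After it: Days 15, 22, 29, 36, 38, 43, 50, 57, 64, 66, 71, 78, 85, 92, 94, 95, 96, 97, 99, 102, 106, 113 and 120 = 23.
- Share before injection: 8/31 = 25.8%. Without the Day 1 baseline: 7/30 = 23.3%.
- Group 2 grid for comparison: Day 1 baseline, then Days 2, 29, 57, 85 and 113; 0 of 5 post-baseline scores precede CAM2038.

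**Dilution.** Assume no change during the run-in and a mean change x after injection.
- Mean change from Day 1, equal weight per assessment: 23x/30 = 0.77x. The plain average of all 31 scores moves by 23x/31 = 0.74x.
- If Days 9 and 93 are also scored, as the footnote's reference to other visits implies: 25x/32 = 0.78x.
- Time-weighted from Day 1 to Day 120: 7/119 = 5.9% of the time precedes injection, giving 112x/119 = 0.94x.

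No weighting is stated, so the range is 0.77x to 0.94x for the change score.

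**TEAE window, Group 3.** For a subject given all four injections, onset must precede Day 92 + 30 = Day 122, so the window is Days 1 to 121.
- SL week by time: 7/121 = 5.8%.
- SL week by clinic visits at which AEs are elicited: 7/33 = 21.2%. This measures how often subjects are asked, not how many events occur.
- Constant hazard h per day (assumed): excess any-TEAE incidence = exp(-114h) - exp(-121h). This peaks at h = ln(121/114)/7 = 0.0085, where incidence is 64.3% over 121 days against 62.1% over 114, a difference of 2.2 points.
- Single preferred term: each subject whose only event of that term falls in the SL week adds 1/16 = 6.25 points.

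The documents give no run-in AE rate. With an assumed 5%, 10% or 20% chance per subject of an event in the SL week, the expected number of subjects with an SL-onset TEAE is 16 × p = 0.8, 1.6 or 3.2. The chance of at least one, 1 - (1 - p)^16, is 56%, 81% or 97%.

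**The case against.** Four arguments on the other side carry weight.

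*The SAP already separates treatments.* SAP 11.0 asks for presentation by the drug actually received, and protocol 9.2.3 treats SL BPN as study drug in Group 3. It would be too strong to say the plan has no relevant rule. But SAP 5.1 uses the same idea to place subjects in groups, and SAP 11.4, the specific AE text, tabulates by treatment group. Neither assigns an event within a subject by its onset. On the as-treated reading, a subject given only SL BPN might be placed under SL BPN, but SAP 11.4 describes no such column, and the number of such subjects may be zero.

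*The SAP shows COWS/SOWS over time.* This stands, and it is the main limit on the point. A reader might infer that a reaction at the switch would be hidden. It would not be: visit-level summaries separate the SL days from later visits, and the dilution arises only if the protocol average is also produced. SAP 11.3 does not say it replaces that average, and it sets no pre-injection baseline.

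*Day 1 is a sensible baseline.* All groups enter on established SL BPN, and for anyone entering on 24 mg the run-in continues the same dose. That supports keeping Day 1, not relying on it alone. Criterion 5 admits Group 3 subjects above 24 mg, who would step down on Day 1; how many is unknown and may be none.

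*The groups are not formally compared.* Group 3 was not randomized, SAP 11.0 makes any formal safety comparison post hoc, and the groups already differ in dose and duration. This is fair, so the point rests on what the Group 3 column means rather than on between-group inference.

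Injection-related TEAEs are tabulated separately and by-subject listings are planned, so the mixing mainly affects systemic events.

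**Conclusion.** The point holds as a moderate clarification. No rule assigns Group 3 TEAEs to SL BPN or CAM2038 by onset, and no pre-injection baseline is set for the scales that monitor the switch. The COWS/SOWS change score is reported at 0.77 to 0.94 of its true size, assuming a flat run-in and depending on an unstated weighting. Any-TEAE incidence rises by at most about 2.2 points, assuming a constant event rate; a single term can move by 6.25 points per affected subject.

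Three stronger readings are not supported. Opening the TEAE window at the first SL dose is not an error, since SL BPN is study treatment here; what is missing is the split at the first injection. The references to a randomization date in SAP 6.1, the worsening clause of SAP 11.4 and Appendix A do not leave Group 3 without a usable date: protocol 9.1 and 9.3 put Group 3 enrollment on Day 1, the day of the first SL dose, so this is a matter of wording. The primary PK analysis is not affected. The lack of a before/after split for urine toxicology in SAP 9.2 is minor: the endpoint is exploratory, and the run-in share is 7/33 = 21% or 2/28 = 7% depending on whether the Day 1 to 6 column means daily samples.

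**What to change.** 1. **SAP 11.4.** Tabulate Group 3 TEAEs by period: onset before the first injection under SL BPN 24 mg; onset or worsening from the first injection under CAM2038 160 mg. Use subjects who started the period as the denominator, and keep a combined Group 3 column. If a partial date cannot place onset on either side of the first injection, assign the event to CAM2038.
2. **SAP 11.3.** Compute any Group 3 COWS/SOWS average from post-injection assessments only, and show the SL run-in separately. Present change from the Day 8 pre-dose value beside change from Day 1. Day 8 should not stand alone: a rise during the run-in that later resolved would then look like improvement on CAM2038.
3. **Optional.** State that the randomization date means the first SL dose date for Group 3. Report Group 3 urine results before and after the first injection, with Day 8 on its own row if its timing relative to the injection is not recorded.

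No visits or samples are added, since Table 3 already schedules these assessments on Days 1 to 8. Protocol 12.1 lets the SAP clarify summary strategies, and SAP 9.3 locks Group 3 separately and later. The cost is a SAP revision and programming before that lock, a second baseline, and one small run-in table for about 16 subjects.
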